3. INTRODUCTION

3.1.Device Description

Overview

EchoMark/EchoMark LP is an ultrasound marker for marking an arteriovenous fistula. The EchoSure diagnostic ultrasound system and its transducer are intended for use in clinical examinations of arteriovenous fistulae and other blood vessels that are marked with an EchoMark/EchoMark LP implant. The system provides measurements and information about blood flow, and conduit diameter, and depth.

EchoMark

EchoMark is an implantable, echogenic, bioresorbable fiducial marker comprised

The EchoMark product line comes in two sizes, EchoMark and EchoMark LP, for physicians to select from. A photo of both sizes compared to a United States Quarter is shown below as **Figure 1**.

The EchoMark is implanted under the vessel of interest during an open surgical procedure. In the context of arteriovenous fistulae, EchoMark implantation will occur during standard open fistula creation procedures through the same incision used for vascular access creation. The surgeon will place the EchoMark LP under the outflow vein of the fistula after the anastomosis of the vein to the artery has been completed. The vessel will sit in the channel of the EchoMark between its two peaks, as shown in **Figure 2**.

he

EchoMark will be secured in place with 3-0 or 4-0 Prolene or equivalent non-resorbable sutures. The EchoMark can be prepared for securing by pre-loading the implant with non-resorbable

sutures. The sutures should be driven through at least two corners of the device at bumper on the lateral edges of the implant at least 1mm from any edge of the EchoMark.

a check is performed to ensure articulation zone, not impinging the elbow motion.

that the devices is outside of the elbow articulation zone, not impinging the elbow motion, secure, and that there is no impingement of the vessel. Afterwards, the incision is closed using standard technique.

Both features provide localization and orientation information about the marked vessel when scanned with the EchoSure ultrasound system that facilitate ultrasound data collection for the quantification of marked vessel's volumetric blood flow rate, diameter and depth.

EchoSure for AVF

EchoSure is a portable semi-automated diagnostic ultrasound imaging device that includes the EchoSure Ultrasound, the EchoSure AVF Application (software) and the EchoSure Probe.

such that the user simply needs to place the probe in the general region of the target rather than in a precise location.

hese features enable health care personnel without

ultrasound experience to quickly and reliably position the EchoSure probe for a successful scan without consideration of technique. A photo of the full EchoSure system is shown in **Figure 3**.

Figure 3 Closeup Photo of EchoSure and EchoSure Probe (left). Photo of full EchoSure system on roll stand (right).

The EchoSure AVF Application is designed with a simple user interface and workflow that walks the user through the scanning process with step-by-step instructions.

With each scan,

EchoSure AVF automatically calculates and reports volumetric flow, diameter and depth of

the AVF. Scan results are presented to the user graphically and with tabulated historical results so changes in flow, diameter and depth can be tracked over time.

3.2 Product Development

3.3 Intended Use

EchoMark is intended to be implanted by the surgeon during upper arm open fistula creation under the outflow vein of the fistula, approximately 3cm away from the anastomosis. EchoSure is intended for use by healthcare personnel, with or without ultrasound training, in dialysis clinics or other clinical settings.

3.4 Indications for Use

The EchoMark/EchoSure System provides measurements and information about blood flow, including volumetric flow rate, diameter, and depth, for assessing upper arm arteriovenous fistulae throughout the maturation period.

3.5 Preliminary Investigations

Benchtop Performance Data

Purpose

Test Procedure

	╸ ╸╴╸	

ISO 10993 biocompatibility testing was performed on the EchoMark device. Results from the tests indicate that the device is non-toxic, non-sensitizing, non-mutagenic and non-irritating therefore biocompatible for its intended use.

EchoSure Probe

Sonavex has also performed extensive biocompatibility testing on EchoSure Probe. Biocompatibility testing of the EchoSure Probe devices was conducted in accordance with ISO 10993 series standards and EP/USP guidance documents as applicable. Additional guidance for the performance of these tests comes from the U.S. FDA June 2016 Guidance Use of International Standard ISO 10993-1, "Biological evaluation of medical devices - Part 1: Evaluation and testing within a risk management process". All tests were conducted in compliance with applicable requirements in the good laboratory practice (GLP) regulations in 21 CFR 58. The specific studies include:

ISO 10993 biocompatibility testing was performed on the EchoSure Probe. Results from the tests indicate that the device is biocompatible for its intended use.

Summary of Outcomes Compared to Literature

In order to evaluate the longer-term impact on outcomes, maturation rates were also evaluated for the subjects in the studies. A total of 34 fistula patients were followed to the first maturation assessment or longer. A summary of the outcomes for EchoMark patients are included below alongside cited literature for non-EchoMark AV fistula patients.

	Sonavex EchoMark Patients ¹	Sonavex EchoMark (>90-day postop) ²	Woodside 2018 (USRDS Data)	Robbin 2018 (HFM Study)	Chan 2018
Number of Patients/AVFs	34	30	45,087	587	146
% Mature	73.5%	83.3%	64%	72%	72%
% Failed	11.8%	16.7%	36%	28%	28%
% Outcome Not Yet Known*	14.7%	N/A	N/A	N/A	N/A

* A maturation determination has either not yet been determined or not yet communicated to Sonavex. ¹ All patients who underwent a first maturation assessment.

² All patients with a maturation outcome assigned or who are at least 90 days post-surgery. Though the national average time to maturation is over 6 months, out of caution, patients who received their AV fistula procedure more than 90 days ago were assigned as 'failure.'

Note: A total of 7 patients had follow-ups occurring after the study was suspended on January 7. These results were communicated to Sonavex verbally and represent 2 mature AVFs, 1 failed AVF, and 4 'outcome not yet known.'

The exact binomial method was used for EchoMark patients with 90-day follow-up to estimate the 95% confidence interval for maturation success. Centered around the 83.3% successful maturation rate, the 95% CI is [65.3% - 94.4%]. Thus, the existing sample size appears adequate to demonstrate that maturation success in the EchoMark patient population is in line with recent large AVF cohort studies^{3,4,5,6,7}. Based on the results above, Sonavex has no reason to believe that EchoMark introduces additional risk to AV fistula patients. In fact, given historic average maturation times of 6-9 months it is likely that many of the patients in "outcome not yet known" may become successes, pushing the maturation success to a level higher than other recent large multicenter reports.

4. OBJECTIVES AND ENDPOINTS

4.1 Objectives

The primary objective of this study is to evaluate the feasibility and safety of the EchoMark and the EchoSure diagnostic ultrasound system for assessing AV fistula blood flow, diameter, and depth.

4.2 Study Endpoints

4.2.1 Primary Safety Endpoints

Composite of new major device related adverse events (MAEs) at 30 days post EchoMark implantation, as adjudicated by the Clinical Events Committee (CEC) including:

- Device or procedure-related death
- Device related infection
- Device related interventions
- Device related hospitalizations
- Fistula failure
- Fistula rupture
- Aneurysm

After the close of the 90-day visit window, all evaluable subjects will be summarized and expansion to a pivotal trial will be requested under a new IDE.

4.2.2 Primary Feasibility (Technical Success):

Rate of Technical Success defined as the successful implantation of the EchoMark implant and the ability to determine blood flow, diameter and depth measurements using the EchoSure diagnostic ultrasound system from baseline to 4 months.

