7.11 Fistula Failure

If the subject's fistula is deemed a failure and abandoned by the investigator, a fistula failure case report form will be completed recording the reasoning for the failure. The subject will remain in the study and receive monthly telephone calls to monitor for adverse events and physical assessments of the EchoMark at all standard of care visits. The subject will complete the 180-day and 12 months visit as scheduled to undergo a physical exam, medical history review, adverse event monitoring, and duplex examination of the EchoMark and exit the study.

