8. RISK AND BENEFIT ASSESSMENT

The study involves the creation of an arteriovenous fistula, therefore the risks of participating in this research include the risks inherently associated with a standard AV fistula creation which may include bruising, numbness, tingling and/or coolness in the extremity, thrombosis, stenosis, failure to mature, additional interventions, venous hypertension, swelling, irritation or pain, bleeding/hemorrhage, hematoma, seroma, wound problem, fever, steal syndrome, ischemia, embolism, infection, increased risk of congestive heart failure, nerve damage, vessel damage, pseudoaneurysm, compartment syndrome, heart problems such as arrhythmias, burns, problems due to sedation or anesthesia, sepsis, allergic reaction, or death.

With the implantation of any foreign material such as a radiologic marker (EchoMark), there is risk of allergic reaction, inflection, inflammation, migration, or extrusion. Given the biocompatibility data collected by the company and the extensive prior use of the material in medicine, the probability of such risk is low. The safety of the device for general use has already been evaluated by the FDA during the clearance process for EchoMark and there has been a prior multicenter study in AV fistula patients that has shown maturation success rates that were in line with recent literature. There is also a possibility that the fistula may slide out of the EchoMark, which may prevent the EchoSure device from measuring the flow, diameter and depth accurately. When the EchoMark implant is secured properly the likelihood of this risk is low and standard of care methods for assessing the fistula are still available making the severity low. There is risk that the ultrasound scan may create mild discomfort for the subject on the wound site. The likelihood and severity of this risk is low.

Prior experience in the AV population captured adverse events including infection and seroma. All subjects are to be closely monitored for signs of an infection or seroma. If the subject begins to exhibit signs of infection, inflammation or extrusion, a clinical decision will be made by the team if the risk from the implantable device requires removal of the device. In these cases, the implantable device will be removed, and the subject will be monitored with the institution's standard of care, including physical exam and possibly ultrasound. The event will be tracked until the symptoms are resolved.

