11.2.8.11 Composite of new major device related adverse events (MAEs) at 12 months

The proportion of subjects with device success and free from deviceand/or procedure-related SAEs (per CEC adjudication) at 12 months. The summaries for each individual safety data point will also be provided. Composite of new major device related adverse events (MAEs) at 12 months post EchoMark LP implantation, as adjudicated by the Clinical Events Committee (CEC), including:

- Device or procedure-related death
- Device related infection
- Device related interventions
- Device related hospitalizations
- Fistula failure
- Fistula rupture
- Aneurysm

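### The primary safety composite is headed device related, but fistula failure, rupture and aneurysm carry no such condition, and section 11.2.6 counts by a third rule

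*Combined protocol and SAP*

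**What the plan says.** The primary safety endpoint in section 4.2.1 is headed "Composite of new major device related adverse events (MAEs) at 30 days post EchoMark implantation, as adjudicated by the Clinical Events Committee (CEC) including" seven items, and the synopsis has the same composite. The items fall into three groups:

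- "Device or procedure-related death", which is wider than the heading because a death related only to the procedure counts;
- infection, interventions and hospitalizations, each with its own device condition (for example "Device related infection");
- "Fistula failure", "Fistula rupture" and aneurysm, with no condition on the item.

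Sections 4.2.3 and 11.2.8.11 repeat the composite at 12 months under the same kind of heading: "Composite of new major device related adverse events (MAEs) at 12 months post EchoMark LP implantation".

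Section 11.2.6, which analyses the 30-day endpoint, does not count these components. It takes the proportion of subjects who have device success and no serious adverse event that the CEC relates to the device or the procedure. Device success is not defined. Section 11.2.8.11 places the same kind of rule beside the 12-month list.

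Other sections bear on the count. Section 7.11 makes failure an investigator's decision ("If the subject's fistula is deemed a failure and abandoned by the investigator"), with the reason recorded but no relatedness test. Section 8 lists "thrombosis, stenosis, failure to mature, additional interventions" among the risks of ordinary fistula creation. Section 9.4 has three relatedness grades and does not say which of them qualify for the composite. Section 12.7 gives adjudication to the CEC under a charter that is not among the documents.

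**The concern.** The heading and the list give different answers for the same event. If the heading limits every item, the separate device labels on infection, interventions and hospitalizations are redundant, and the wording for death contradicts the heading. If the labels are deliberate, the three unlabelled items count whatever their cause, and the title of the composite is wrong. Both readings are reasonable.

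This matters because the trial has one arm. Fistulas fail without a marker, and no control rate separates background failure from failure that the marker causes. The any-cause reading reports background failure under a device-related title. The attributed reading depends on case-by-case judgement. If the choice is made after events are known, the primary safety figure depends on a decision that the plan did not fix.

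**Working it through.** **1. The rules side by side.** Take a subject whose only event is the one in the row. For 11.2.6, assume that device success is met and that the procedure means the index procedure, at which the fistula is created and the marker implanted.

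| Event | 4.2.1 by heading | 4.2.1 by item list | 11.2.6 |
|---|---|---|---|
| Fistula failure attributed to the marker, serious | counts | counts | counts |
| Fistula failure attributed to the marker, not serious | counts | counts | does not count |
| Fistula failure attributed to the procedure only, serious | does not count | counts | counts |
| Fistula failure related to neither | does not count | counts | does not count |
| Death related to the procedure only | does not count | counts | counts |

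The rules agree only in the first row. Rupture and aneurysm behave as fistula failure does.

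**2. The heading reading is itself not fixed.** In section 9.4, a temporal relationship is enough for the grade Related, and every failure follows implantation in time. An established alternative cause leads to Not Related. Whether Possibly Related qualifies is not stated.

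**3. The documents' own figures.** The sample size section has no calculation for this composite. The only failure rates are in the outcome table of section 3.5. Its EchoMark figures reproduce: 4/34 = 11.8% failed and 5/30 = 16.7% failed. The exact (Clopper-Pearson) 95% interval for 25/30 = 83.3% mature is 65.3% to 94.4%, as stated. The cited cohorts without the marker show 28%, 28% and 36% failed.

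**4. Effect of one subject.** With N = 20 (section 11.1, the planned maximum), 1/20 = 5 percentage points. Exact 95% intervals:

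- 0/20 = 0% (0 to 16.8%)
- 1/20 = 5% (0.1 to 24.9%)
- 2/20 = 10% (1.2 to 31.7%)
- 3/20 = 15% (3.2 to 37.9%)

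**5. Chance that the reading matters.** Let p be the assumed proportion of subjects with a failure not attributed to the device by the analysis time. Assume that subjects are independent and that such a subject has no other counted event. The expected number is 20p, and P(at least one) = 1 − (1 − p)^20. The documents give no 30-day value of p, so a range is shown.

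| p (assumed) | Expected subjects | P(at least one) |
|---|---|---|
| 2% | 0.4 | 33% |
| 5% | 1.0 | 64% |
| 10% | 2.0 | 88% |
| 15% | 3.0 | 96% |

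**6. Upper bound at 12 months.** Applying the section 3.5 rates to 20 subjects gives 20 × 0.118 = 2.4, 20 × 0.167 = 3.3, 20 × 0.28 = 5.6 and 20 × 0.36 = 7.2 failures. If none were attributed to the device, the two readings would differ by 11.8 to 36 percentage points. This is a ceiling for the 12-month composite only.

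**The case against.** The strongest reply is that the trial is a descriptive feasibility study in which either version can be rebuilt. Sections 11.2.6 and 11.2.8.11 promise a summary of each safety item. Section 9.5 records all adverse events regardless of relationship, section 7.11 records the reason for each failure, and section 11.2.1 provides subject listings. The CEC charter may also contain a counting rule. Much of this stands. It limits the harm, and it means that a failure would not vanish from the report under either reading. It does not say which figure is the primary result, and a row for fistula failure has the same ambiguity unless it is labelled any-cause or attributed.

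A reader might infer stronger claims that the documents do not support:

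- *The plan has no relatedness condition at all.* It has one in the heading and another in 11.2.6. The problem is that these and the item list disagree.
- *Fistula failure is the most frequent component.* The section 3.5 table gives only mature, failed and not yet known. It has no rates for the other components and ranks nothing.
- *The safety figure taken to the pivotal request could move by 12 to 36 points.* Those rates are maturation failure, which is not the same event as abandonment under section 7.11. For the 16.7% figure, unresolved patients more than 90 days after surgery were classed as failures. The request also follows the 90-day visit window, before 12-month data are complete.

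**Conclusion.** The point holds as a conflict between stated rules, not merely as missing detail. The heading, the item list and section 11.2.6 can give different primary safety counts from the same adjudicated events, and no text in the documents decides between them.

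The size at 30 days is 5 percentage points per reclassified subject if N = 20. The 64% and 88% chances rest on assumed non-device failure rates of 5% and 10%; at 2% the chance is 33%. The 2.4 to 7.2 failures bound the effect on the 12-month observational composite and should not be read as the expected shift. The plan tests no hypothesis, so neither type I error nor power is involved. What is affected is the meaning of the reported rate and whether it was fixed in advance. The plan should be changed, although item summaries and listings soften the consequence.

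**What to change.** Align the synopsis and sections 4.2.1, 4.2.3, 11.2.6 and 11.2.8.11 on one definition. Report two lines at both 30 days and 12 months from the same adjudicated data:

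- **(a) Any cause:** fistula failure, rupture or aneurysm from any cause, plus the four components that already carry a condition, under a heading that does not say device related.
- **(b) Attributed:** all seven components only when the CEC attributes them to the device, keeping the existing wider condition for death so that procedure-related deaths are not lost.

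State which grades in section 9.4 count as related, including whether Possibly Related does. Name the primary line before CEC adjudication starts. The mention of reconsent in section 7.9 suggests that subjects may already be enrolled. If adjudication has begun, name the line before any further analysis.

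The cost is revised wording and one extra table row. No new data are needed, because failure reasons are recorded and the CEC already adjudicates reported events. The downside is that the any-cause line will probably look less favourable than an attributed figure alone.

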5. STUDY DESIGN

5.1 Overall Design

This is a prospective, multi-center, single-arm, non-blinded clinical trial designed to evaluate the feasibility and safety of the Sonavex EchoMark and the EchoSure in subjects undergoing new upper arm autologous arteriovenous fistula creation who require hemodialysis. The trial will enroll up to 20 subjects in up to 6 clinical sites in the United States. Each site can enroll up to 3 "roll-in" subjects. Roll-in subjects will be consecutive, must be identified as roll-in subjects prior to the EchoMark implantation, and will not count toward the total enrollment of 20 subjects.

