11. STATISTICAL ANALYSIS

11.1. Sample Size Considerations

This is a feasibility study and accordingly there is not a pre-specified null hypothesis to be tested against for the study endpoints. Data collected from this study will provide preliminary device safety and effectiveness data for the use of the EchoMark/EchoSure System in patients receiving arteriovenous fistulae for hemodialysis access. Descriptive statistics will be reported for the study data. Inferential statistical analysis will be conducted in an exploratory manner. The sample size for this study is planned to be up to 20 subjects at up to 4 investigational sites, with data points collected at multiple timepoints for each subject.

Statistical methods for the study are outlined below.

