11.2.7 Analysis of Primary Feasibility (Technical Success)

Definition of feasibility endpoints are described in Section 4.2.

For composite endpoints, i.e., technical success and implantation success, the number and percentage of subjects with success will be summarized. Descriptive statistics for components of each endpoint will also be provided.

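### The 90-day summary behind the pivotal request covers an undefined evaluable set, and neither primary endpoint has a planned confidence interval

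*Combined protocol and SAP*

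**What the plan says.** Section 4.2.1, and the synopsis in nearly the same words, tie the next development step to a summary at the close of the 90-day window: "all evaluable subjects will be summarized and expansion to a pivotal trial will be requested under a new IDE". The word evaluable is not defined there or anywhere else.

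Section 11 describes two other sets. Section 11.2.1 bases the primary analysis on whatever data exist for all enrolled subjects, and 11.2.2 counts a person as enrolled from the signing of consent. Section 11.2.4 limits the primary and observational samples to enrolled subjects whose implantation succeeded. Neither mentions roll-ins, which Section 5.1 allows at up to 3 per site and which "will not count toward the total enrollment of 20 subjects".

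For the primary safety endpoint, 11.2.6 plans a proportion at 30 days. For technical success, 11.2.7 says that "the number and percentage of subjects with success will be summarized". Neither names an interval. Section 11.1 states that "there is not a pre-specified null hypothesis to be tested against for the study endpoints" and adds that "Inferential statistical analysis will be conducted in an exploratory manner", without naming a method. For the sponsor's earlier patients, however, Section 3.5 reports: "The exact binomial method was used for EchoMark patients with 90-day follow-up to estimate the 95% confidence interval".

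**The concern.** The 90-day summary is what the sponsor will carry into a request for a pivotal trial, so its denominator and its precision both matter.

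**Denominator.** Three sets are in play and they differ. The plan's own rules produce subjects who may have no 90-day data. An explanted subject is followed until the event resolves and then exits (7.12). A subject with an abandoned fistula stays in the study but moves to telephone calls, with study visits named only at 180 days and 12 months (7.11). A subject who cannot be reached is treated as withdrawn (10.3). Missing values are not imputed (11.2.10). The first two groups are largely the device's or the access's poor outcomes, so a literal 90-day evaluable set could omit the cases that the safety summary exists to show.

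**Precision.** With about 20 subjects, an empty event table or a full success table is easily over-read unless its confidence limit is printed beside it.

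**Working it through.** **Inputs.** Main cohort: up to 20 (5.1, 11.1). Roll-ins: up to 3 per site. The documents disagree on sites: Section 11.1 has "The sample size for this study is planned to be up to 20 subjects at up to 4 investigational sites", while Section 5.1 has "The trial will enroll up to 20 subjects in up to 6 clinical sites in the United States". Roll-ins could therefore number 3 × 4 = 12 or 3 × 6 = 18, giving pooled totals of 32 or 38. Interval method: exact binomial (Clopper-Pearson), two-sided 95%, carried over from Section 3.5.

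**Step 1: reproduce the plan's own figure.** 83.3% of 30 is 25/30. The lower limit is the 0.025 quantile of Beta(25, 6) = 65.28%. The upper limit is the 0.975 quantile of Beta(26, 5) = 94.36%. Section 3.5 gives 65.3% to 94.4%, so the method is confirmed.

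**Step 2: zero events.** The upper limit is 1 − 0.025^(1/n).

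| n | Situation | Upper limit for 0/n |
|---|---|---|
| 15 | five of 20 not counted | 21.8% |
| 18 | two of 20 not counted | 18.5% |
| 20 | full main cohort, no roll-ins | 16.8% |
| 32 | 20 plus 12 roll-ins | 10.9% |
| 38 | 20 plus 18 roll-ins | 9.3% |

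The mirror image holds for success: 20/20 has a lower limit of 100% − 16.8% = 83.2%. This applies to technical success and also to 11.2.6, which counts event-free subjects, so that a clean result there reads as 100% rather than 0%.

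**Step 3: a few events.** 1/20 = 5%, limits 0.1% to 24.9%. 2/20 = 10%, limits 1.2% to 31.7%. Equivalently, 18/20 successes = 90%, limits 68.3% to 98.8%.

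**Step 4: how often a clean table hides a real rate.** For illustration, a true rate of 10% gives 0/20 with probability 0.90^20 = 12.2%, and a true rate of 5% with probability 0.95^20 = 35.8%.

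**Step 5: what the choice of set can do.** Suppose two of 20 subjects have an event and neither has 90-day data. Counting everyone gives 2/20 = 10%, upper limit 31.7%. Dropping the two gives 0/18 = 0%, upper limit 18.5%. This is a hypothetical illustration and not a forecast.

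**Step 6: timing of technical success.** The 90-day window closes at day 90 + 15 = 105. Technical success runs to 4 months (4.2.2), and that visit falls between day 120 − 15 = 105 and day 120 + 15 = 135. At the cut, the last subjects will generally lack a complete technical-success result, and the plan does not say how to count them.

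**Step 7: denominator for technical success.** Section 4.2.2 makes successful implantation part of the endpoint. Section 6.6 treats a consented subject who never receives the marker as a replaceable screen failure, and 11.2.4 leaves out unsuccessful implantations. A failed attempt therefore cannot lower the rate that is meant to count it.

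**The case against.** The strongest reply is that this is openly a descriptive feasibility study. No hypothesis is required, exploratory inference is allowed, and any reader can form an interval from the counts in 11.2.7 and the subject listings in 11.2.1. Section 11.2.9 places an interim analysis at the same 90-day point, and the sets in Section 11 might be taken to govern it. Failed-fistula subjects and those whose fistula lies outside the marker remain in the study (7.10, 7.11), explants are reported within 24 hours (9.5), and the CEC adjudicates all reported events (12.7).

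Much of this stands, and it rules out several stronger readings:

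- A reader might infer that only percentages will be shown. Section 11.2.7 plans counts too; what is missing is the interval.
- A reader might infer that the request goes ahead whatever the data show, and that a go/no-go threshold is required. The sentence in 4.2.1 does carry no condition. But Section 10 lists unacceptable risk as a ground for termination, and the DSMB must recommend continuing or terminating at each meeting. In a declared feasibility study a numerical threshold is a preference, and the documents give no event rate from which to set one.
- A reader might infer that the plan intends to drop poor outcomes. It does not say so. The undefined term merely permits it.
- A reader might take 17% as the fixed limit. It applies only to 20 counted subjects without roll-ins.

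The reply leaves two gaps: the term in 4.2.1 is undefined and competes with two sets in Section 11 that themselves differ, and the standard of reporting in Section 3.5 is not carried forward.

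**Conclusion.** The point holds as one of definition and reporting. The set behind the 90-day summary is undefined and inconsistent with 11.2.1 and 11.2.4, and on one natural reading it could omit explanted, exited or lost subjects. No interval is planned for either primary endpoint.

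For a clean result in the full main cohort, the unreported uncertainty reaches 16.8% for events, or down to 83.2% for success. It widens if fewer than 20 are counted and narrows to between 10.9% and 9.3% if the maximum number of roll-ins is pooled. These limits assume the two-sided 95% level that reproduces the interval in Section 3.5. For 0/20, a one-sided 95% bound would be 13.9% and a Wilson two-sided limit 16.1%, so the choice of method does not change the message.

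**What to change.** - **Section 4.2.1 and synopsis, safety:** replace the evaluable set with all subjects who received an EchoMark LP. Count explanted, failed and exited subjects, show the number with missing 30-day data, and report roll-ins separately from the 20.
- **Technical success:** use all subjects in whom implantation was attempted. In the 90-day summary, mark those who have not reached 4 months as incomplete, counting them neither as successes nor as exclusions.
- **Sections 11.2.1 and 11.2.4:** reconcile the two descriptions with these sets, and say where roll-ins belong.
- **Sections 11.2.6 and 11.2.7:** report n/N with an exact two-sided 95% confidence interval.
- **Section 11.1:** state the precision that 20 subjects give, for example an upper limit of 16.8% for 0/20.

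The definitions should be settled before the 90-day data are summarized. The cost is protocol and SAP wording, with no added subjects or visits. The one drawback for the sponsor is that the reported result will look slightly less favourable.
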